Perceived message effectiveness	Wave 4	Week 5
Message credibility	Wave 4	Week 5
Eye-tracking		Weeks 1-4
Biomarkers		Weeks 0, 5
Outcomes		
Nicotine beliefs	Waves 1, 2, 4	Weeks 0, 2, 5
Intention to use nicotine/tobacco products	Waves 1, 2, 4	Weeks 0, 2, 5
Nicotine/tobacco use and behavior	Waves 1, 2, 4	Weeks 0, 2, 5
Subjective rating of study cigarette		Weeks 1-5
Manipulation check	Waves 1, 2, 4	Weeks 0, 2, 5
Moderators		
Sociodemographics	Wave 1	Week 0
Literacy	Wave 1	Week 0
Cancer risk beliefs	Wave 1	Week 0
Cancer risk behaviors	Wave 1	Week 0
Fagerstrom test for nicotine dependence	Wave 1	Week 0
Other key constructs		
Attitudes about nicotine	Waves 1, 2, 4	Weeks 0, 2, 5
Nicotine-related norms	Waves 1, 2, 4	Weeks 0, 2, 5
Behavioral control	Waves 1, 2, 4	Weeks 0, 2, 5
Stages of change	Wave 1, 4	Week 0, 5
Policy support	Wave 4	Week 5

Statistical Analysis Plan

Sample Size. Power for Aim 1 was calculated for 715 adults with 70% retention at 12-weeks follow-up. Our pilot data provide estimates of the magnitude of the effect of the Nicotine Corrective Messaging (NCM) intervention on the primary outcome of nicotine beliefs, including four continuous scales on nicotine false beliefs, NRT false beliefs, e-cigarette false beliefs, and reduced nicotine content (RNC) cigarette false beliefs.¹ With an expected final sample size of 500 and ignoring repeated measures, we will have 80% power to detect differences of <1 unit between the intervention and control group means for the nicotine, NRT, and e-cigarette false belief scales and a 1.64 difference in the group means for the RNC cigarette false beliefs scale. These equate to small-to-medium effect sizes (Cohen's *d* ranging from 0.25 to 0.27), which are smaller than the effects observed for nicotine and NRT false beliefs outcomes in the pilot study.¹

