Data Preparation. Prior to performing all analyses, standard data screening/cleaning procedures will be applied. These procedures will (1) screen the data for data recording errors, (2) check for outliers, (3) assess the extent and pattern of missing data, and (4) check that appropriate assumptions of normality are met whenever necessary. In all analyses, the assumptions underlying the application of all the statistical methods that are used will be examined, principally using standardized residuals, influence diagnostics, and graphical displays. Where needed, appropriate transformations will be applied to ensure that data meet model assumptions. Descriptive analyses will characterize participants overall and by study condition. Bivariate tests will assess for differences in participant characteristics by intervention condition (NCM vs. control) and examine if any baseline variables that are imbalanced between study groups are associated with primary and secondary outcomes (*p* < .10). Any such variables will be accounted for in analyses as covariates.

Analytic Approach.

Aim 1: Test the impact of nicotine corrective messaging (NCM) on nicotine beliefs and the subsequent impact on intention and use of tobacco and nicotine products in a national sample of 715 adult smokers and non-smokers followed for 12 weeks.

Hypothesis 1a: Adults in the NCM condition will report fewer false beliefs about nicotine, NRT, e-cigarettes and RNC cigarettes and lower intentions to use tobacco and nicotine products at follow-up compared to those in the control condition.

Hypothesis 1b: Current smoking will moderate the effect of NCM on false beliefs of nicotine, NRT, e-cigarettes, and RNC cigarettes and intended use of tobacco and nicotine products at follow-up. The effect of NCM on these outcomes will be attenuated in adult smokers compared to non-smokers.

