Analyses for Aims 1 and 2 employ common measures and a common analytic framework to test the impact of nicotine education on nicotine beliefs and behavior. Primary analyses will use an intention-to-treat approach. We will conduct sensitivity analyses with different assumptions for the missing data mechanism including analyzing complete data only⁹ and last observation carried forward. Outcomes for Aim 1 focus on continuous measures (*primary outcome*: nicotine beliefs; *secondary outcomes*: frequency of nicotine/tobacco use), with the primary hypotheses (**Hypotheses 1a**) focused on the effect of the intervention on these outcomes. Preliminary analyses will examine differences in these outcomes across study conditions at the first post-exposure time point (Wave 2) and at the final timepoint (Wave 4) controlling for covariates that are differentially distributed between study groups. In Aim 1, we will also use multiple logistic regression models to examine effects of the NCM intervention on the proportion of participants reporting specific nicotine beliefs (i.e., "nicotine is a cause of cancer"), intentions to use cigarettes, e-cigarettes, NRT, and low nicotine cigarettes in the next 12 months, and

tobacco/nicotine use (e.g., any new use/trial, any past 30-day use, product-specific past 30-day use).

For **Hypothesis 1b**, we will evaluate whether current smoking moderates the effect of NCM on our primary and secondary outcomes by incorporating an interaction between study condition (NCM/control) and current smoking status (smoker/non-smoker) through the following steps: 1) bivariate analyses, to determine if outcomes vary by these variables; 2) testing whether current cigarette smoking moderates ($p < .05$) experimental effects in the models above by the addition of a study condition-by-smoking status interaction term into the model; 3) if no evidence of moderation exists, including cigarette smoking as a covariate.

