Exploratory analyses will focus on three areas: 1) potential moderators of the relationship between intervention condition and the study outcomes; 2) nicotine beliefs as a potential mediator of the relationship between intervention condition and constructs identified in the Theory of Planned Behavior (i.e., nicotine-related attitudes, norms, behavioral control, and nicotine/tobacco intentions and use); and 3) the relationship between visual attention to nicotine education messages and nicotine beliefs in the participants exposed to the NCM intervention.

For the first area (*moderation*), we will conduct exploratory analyses using the same steps described for Hypothesis 1b to determine whether there are potential moderators of the relationship between the intervention(s) and outcomes, specifically age, gender, literacy, baseline cancer beliefs and cancer risk behaviors.

For the second area (*mediation*), we will draw from traditional mediation frameworks and use robust methods to explore the relationships outlined in our theoretical framework, specifically whether changes in nicotine beliefs post-exposure (Wave 2) influence nicotine-related attitudes, norms, behavioral control, intention, and behavior at the final assessment (Wave 4). We will examine whether nicotine beliefs at Wave 2 are associated with these outcomes using bivariate statistics and regression-based analysis accounting for any covariates as described above. Where these preliminary steps indicate potential correlation between nicotine beliefs and study outcomes ($p < .05$), we will test for mediation by estimating the indirect effects of nicotine beliefs on follow-up outcomes via the intervention condition using a bias-corrected bootstrapping method with 1,000 resamples. This approach estimates indirect (i.e., mediation) effects and produces bias-corrected asymmetric 95% CIs correcting for non-normality of the distribution of indirect effects and providing higher power and better control over the Type I error rate versus traditional approaches to test mediation. Asymmetric 95% confidence intervals around indirect effect estimates for nicotine beliefs that do not include zero will be interpreted to indicate significant mediation.

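### The mediation models usually leave out Wave 1 beliefs and the Wave 1 outcome, so they can declare mediation where none exists

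*Combined protocol and SAP*

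**What the plan says.** The mediation paragraph under Exploratory analyses sets out to learn "whether changes in nicotine beliefs post-exposure (Wave 2) influence nicotine-related attitudes" and other Wave 4 constructs. The modelling sentence that follows uses a level instead: "We will examine whether nicotine beliefs at Wave 2 are associated with these outcomes". No change score is defined. Covariates enter by cross-reference, "using bivariate statistics and regression-based analysis accounting for any covariates as described above".

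Two rules stand above that point:

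- **Data Preparation** will "examine if any baseline variables that are imbalanced between study groups are associated with primary and secondary outcomes", with p < .10, and adjusts for variables that pass.
- **Hypothesis 1b** puts smoking in the model as an interaction or, "if no evidence of moderation exists, including cigarette smoking as a covariate".

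If beliefs and an outcome are associated at p < .05, the indirect effect is tested by a bias-corrected bootstrap with 1,000 resamples. A 95% interval that excludes zero is taken as significant mediation. The sentence describing this test has the effect of beliefs passing through study condition, although the opening of the Exploratory analyses section names beliefs as the mediator.

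The Study Measures table lists beliefs, attitudes, norms, behavioral control, intention and use at Waves 1, 2 and 4.

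**The concern.** Randomization protects the path from condition to beliefs. It does not protect the path from beliefs to outcomes. Someone whose false beliefs already went with a given attitude or use pattern at Wave 1 will tend to show the same pairing later, whether or not beliefs cause anything. Multiplying that inherited association by a real NCM effect on beliefs gives a non-zero indirect effect.

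A screen on arm imbalance does not look for such confounders. It also tests association with the primary and secondary outcomes, which the Analytic Approach names as beliefs and frequency of use. Attitudes, norms and behavioral control are not among them.

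At stake is the claim that NCM acts on attitudes, intentions or use by correcting beliefs.

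**Working it through.** **The plan's own figures.** Sample Size: 715 × 0.70 = 500.5, which agrees with "With an expected final sample size of 500". With 250 per arm, d = 0.25 and two-sided alpha 0.05 (assumed), power = Φ(0.25 × √125 − 1.96) = Φ(0.835) = 79.8%, which reproduces the stated 80%. The plan gives d "ranging from 0.25 to 0.27"; 0.25 is used below as the effect of NCM on beliefs.

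**How often the Wave 1 terms are left out.** Taking p < .10 as the imbalance threshold (assumed), each Wave 1 variable is imbalanced in about 10% of randomizations. Both are omitted in 0.9 × 0.9 = 81% of trials if independent, and in 90% if perfectly correlated. Simulations gave 76–89%.

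**Model with no true mediation.** Wave 2 belief = s × Wave 1 belief + 0.25 × condition + noise. Wave 4 outcome = s × Wave 1 outcome + noise. Variances are 1 within arm, s is stability and r is the Wave 1 belief–outcome correlation. Neither s nor r is in the documents. Smoking is not simulated in the main grid, so r there means the correlation left after smoking.

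**Hand check, s = 0.6, r = 0.3, no covariates.**

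- *Wave 2 level.* Spurious coefficient = s²r = 0.6 × 0.6 × 0.3 = 0.108. Power of the belief–outcome test ≈ Φ(0.108 × √500 / √(1 − 0.108²) − 1.96) = 68%. Both paths significant: 0.80 × 0.68 ≈ 54%; simulated 56%.
- *Change score.* Covariance with the outcome = 0.108 − 0.6 × 0.3 = −0.072; variance of the change = 2 − 2 × 0.6 = 0.8; coefficient = −0.072/0.8 = −0.09. The path powers are 88% and 44%, product ≈ 38%; simulated 40%.

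The two readings of the mediator therefore give false effects of opposite sign. Mean simulated indirect effects were +0.022 and −0.019.

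**Simulated false mediation, Data Preparation rule applied** (1,000 trials per setting, 400 for logistic; N=500; Pearson p < .05 screen; bias-corrected interval; Monte Carlo SE at most 1.6 points, 2.5 for logistic):

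| Setting | r=0.1 | r=0.2 | r=0.3 | r=0.4 |
|---|---|---|---|---|
| Level, s=0.4 | 5% | 9% | 13% | 20% |
| Level, s=0.6 | 9% | 27% | 48% | 64% |
| Change score, s=0.6 | – | 15% | 35% | 47% |
| Logistic, s=0.6 (30% prevalence assumed) | – | 17% | 34% | 48% |

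The logistic row is included because the SAP says "we will also use multiple logistic regression models to examine effects of the NCM intervention" on binary intention and use.

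**Where the problem vanishes or shrinks (level, s=0.6).** r=0: 4%. d=0 with r=0.3: 3%. With smoking in the model (50% prevalence assumed) and explaining all of r=0.3: 3%; explaining half of r: 14% at r=0.2 and 22% at r=0.3.

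**Separately coded checks with smoking always in the model.** With r measured beyond smoking and set at 0.3, false mediation was 26% (s=0.5), 52% (s=0.6) and 63% (s=0.7).

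**With both Wave 1 terms in the outcome equation:** 1–6% in every d=0.25 setting where they were tested with error-free measures. With reliability 0.7 and r=0.2/0.3/0.4, 6/8/8% remains if only Wave 1 is measured with error and 8/14/23% if all measures are. Wave 1 belief alone suffices only when it is error-free; with Wave 1 reliability 0.7 it leaves 9/17/22%.

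**The case against.** The strongest case on the other side has four parts.

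- **Smoking is in the model.** It enters as a covariate or through the interaction, and it may carry much of the baseline correlation. This stands as a limit on size: if smoking explains half of r, 48% becomes 22% at r=0.3. It removes the problem only if smoking explains all of r.
- **The inputs are assumed.** Stability and r are not in the documents, and d = 0.25 is a detectable difference, not a forecast. Sample Size says pilot effects were larger only for nicotine and NRT beliefs. The simulated screen was an unadjusted correlation, whereas the SAP also mentions adjusted regression; a check using an adjusted screen gave rates of the same order. The mechanism stands; the exact rate is not known.
- **The remedy has costs and gaps.** With a true belief effect of 0.1 SD per SD, power fell from 76–83% to 55–57%, mainly because bias that had counted as power was removed. With reliability 0.7 in all measures the adjusted estimate was 0.034–0.035 against a true 0.050. Any new use has no Wave 1 value of its own.
- **The analysis is exploratory, and the SAP speaks of robust methods.** The first is true and limits the weight. The second is undefined, and a bootstrap addresses non-normality, not confounding.

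The reversed sentence is a wording slip, but the mediator definition is a real ambiguity because the sign of the bias depends on it.

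**Conclusion.** The concern holds. As written, the mediation models usually omit the two baseline variables most directly suited to controlling confounding of the belief-to-outcome path, and the decision rule can then report mediation that is not there. This needs both an NCM effect on beliefs, which is the trial's own hypothesis, and a baseline belief–outcome correlation beyond smoking. If either fails, the false rate is near or below 5%.

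Confidence in the defect is high; confidence in its size is moderate, since it rests on assumed stability and correlation. It should be corrected, but it bears only on the mechanistic claims.

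**What to change.** Amend the mediation paragraph as follows.

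1. State whether the mediator is the Wave 2 level or the change in beliefs.
2. Always include Wave 1 beliefs and the Wave 1 value of the outcome in the outcome equation, with current smoking and any variable passing the Data Preparation screen. For a derived outcome such as new use, take baseline use instead. The belief coefficient is then the same for level and change. The same terms in the condition-to-belief equation are optional, for precision.
3. Reword the reversed sentence as the indirect effect of condition on each Wave 4 outcome through Wave 2 beliefs.
4. Keep the bootstrap, but report an interval excluding zero as exploratory evidence consistent with mediation, since measurement error and unmeasured confounding can remain.

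The cost is SAP wording and two terms in one equation; the constructs are already measured at Wave 1. In one setting with real mediation (belief effect 0.2 SD per SD, s=0.6, r=0.3), power was 83% under the plan's rule and 82% with the added terms. The mean estimate moved from 0.070 to 0.049, against a true 0.25 × 0.2 = 0.050.

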The Nicotine Corrective Messaging (NCM) intervention condition was based on messages tested in our team's pilot study.¹ It included the following six original messages and two new messages addressing nicotine in cigarette and e-cigarette products that were adapted from several evidence-based sources to be more accessible to a lay audience. The sources consisted of FDA's 2017 comprehensive plan for tobacco and nicotine regulation,² FDA's 2013 modifications to labeling of NRT products for over-the-counter human use,³ the 2014 U.S. Surgeon General's Report on the Health Consequences of Smoking,⁴ reports on carcinogens from the International Agency for Research on Cancer,⁵⁻⁷ and the NASEM report on the "Public Health Consequences of E-cigarettes.⁸ Participants in the NCM condition were exposed to all eight messages in the same order at each exposure.

Upon study enrollment, participants completed baseline questions about tobacco use behavior, nicotine beliefs, and other measures (see Study Measures). After completing the baseline survey, participants were randomly assigned in equal numbers to the Nicotine Corrective Messaging (NCM) intervention condition or the delayed message control condition. Participants in the NCM condition then received their first exposure to the study messages. Participants viewed each image in the NCM condition for at least 5 seconds, and we assessed self-reported visual attention using a heatmap task. We allowed for three weeks to maximize the collection of Wave 1 (Weeks 1-3) and Wave 4 (Weeks 10-12) data and two weeks for Wave 2 (Weeks 4-5) and Wave 3 (Weeks 7-8). In the Wave 2 survey (Weeks 4-5), all participants completed measures of nicotine beliefs and intentions/use of nicotine and tobacco products; this provided the first post-exposure measures of the key outcomes. Participants in the NCM condition then received their second exposure to study messages and completed the heatmap task. Only participants in the NCM condition received the Wave 3 survey (Weeks 7-8), which comprised the third exposure to study messages and the heatmap task. The Wave 4 survey (Weeks 10-12) included the final survey assessment of key measures, followed by exposure to NCM messages and heatmap task for all participants.

Study Measures

	Aim 1: Population study	Aim 2: Lab study
Intervention/Exposure		
Nicotine messaging vs. control	Wave 1	Week 1
Normal nicotine vs. RNC cigarette		Week 1
Heatmapping	Waves 1-4	

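### The SAP's mediation sentence makes the randomised condition the mediator, against the plan's own statement that nicotine beliefs mediate; followed literally, it estimates a different quantity

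*Combined protocol and SAP*

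**What the plan says.** All of the mediation text is in the Statistical Analysis Plan, under Analytic Approach, in the paragraphs on exploratory analyses.

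- The opening list gives the second exploratory area as "nicotine beliefs as a potential mediator of the relationship between intervention condition and constructs identified in the Theory of Planned Behavior".
- The mediation paragraph then asks whether belief changes at Wave 2 influence attitudes, norms, behavioural control, intention and behaviour at Wave 4.
- A screening step comes first. The test is run "Where these preliminary steps indicate potential correlation between nicotine beliefs and study outcomes", at p < .05.
- The estimation sentence then specifies "estimating the indirect effects of nicotine beliefs on follow-up outcomes via the intervention condition using a bias-corrected bootstrapping method", with 1,000 resamples.
- The decision rule is: "Asymmetric 95% confidence intervals around indirect effect estimates for nicotine beliefs that do not include zero will be interpreted to indicate significant mediation".

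The Study Protocol section fixes the timing. On allocation: "After completing the baseline survey, participants were randomly assigned in equal numbers to the Nicotine Corrective Messaging (NCM) intervention condition" or the delayed-message control. On the first post-exposure measurement: "In the Wave 2 survey (Weeks 4-5), all participants completed measures of nicotine beliefs". Aim 1 gives the same order: messaging, then beliefs, then intention and use.

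**The concern.** In the phrase *indirect effect of A on B via C*, C is the mediator. The estimation sentence therefore describes a path from beliefs through condition to outcome. The opening list, Aim 1 and the visit schedule all describe a path from condition through beliefs to outcome. A random assignment made at Wave 1 cannot carry an effect of beliefs measured at Wave 2.

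The sentence that is wrong is the one that tells the analyst what to compute. The SAP gives no model equations to settle the direction. The decision rule mentions only indirect effect estimates for nicotine beliefs, which can be read either way. An analyst who follows the sentence tests the wrong quantity, and one who silently corrects it departs from the written plan. At stake is the plan's exploratory answer on whether the messages work by changing beliefs. The SAP also says that Aims 1 and 2 share an analytic framework, so the wording could carry over to the lab study.

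**Working it through.** **Inputs from the documents.** Expected final sample 500; equal allocation; detectable d of 0.25 to 0.27 (Sample Size). Bias-corrected bootstrap with 1,000 resamples, 95% interval, and p < .05 screening on the belief–outcome association (exploratory analyses). The plan states no mediation figure to reproduce. Its sample-size figures do reproduce: 715 × 0.70 = 500.5, and with 250 per arm the detectable d at 80% power, two-sided 5%, is (1.960 + 0.842) × √(2/250) = 0.251.

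**Assumptions.** Let x be the arm (0/1, half each, variance 1/4), m = a·x + e₁ the Wave 2 beliefs, and y = b·m + c·x + e₂ a continuous Wave 4 outcome, with unit error SDs. The path sizes a, b and c are not in the documents. The value a = 0.25 is borrowed from the plan's detectable d.

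**Step 1: what each wording estimates.**

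- Intended: (slope of m on x) × (slope of y on m given x) = a·b.
- As written: (slope of x on m) × (slope of y on x given m) = [(a/4) / (1 + a²/4)] × c.

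The belief-to-outcome path b does not appear in the second product. In its place is c, the part of the effect that beliefs do not carry.

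**Step 2: size and sign under partial mediation.**

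- a = 0.25, b = c = 0.30: intended 0.25 × 0.30 = 0.075; as written (0.0625/1.0156) × 0.30 = 0.0185. The ratio is 0.25. Simulated means: 0.076 and 0.018.
- a = −0.5, b = 0.30, c = −0.30: intended −0.150; as written (−0.125/1.0625) × (−0.30) = +0.035. Simulated means: −0.151 and +0.034.

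The ratio is (c/b) × (1/4)/(1 + a²/4), so the factor of about a quarter assumes b and c of equal size. The sign is wrong whenever b and c have opposite signs. That happens if the messages lower false beliefs (a < 0) and the direct and indirect effects act in the same direction.

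**Step 3: how often mediation is declared.** N = 500, bias-corrected bootstrap, 1,000 resamples, 400 trials per row. Screening is taken as p < .05 on the bivariate belief–outcome association.

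| Scenario (a, b, c) | Intended path | As written |
|---|---|---|
| Complete mediation (.25, .30, 0) | 81% | 7% |
| Complete mediation (.40, .30, 0) | 99.5% | 8% |
| Partial (.25, .30, .30) | 83% | 80% |
| Partial (−.27, .30, −.30) | 85% | 80% |
| Partial (−.5, .30, −.30) | 100% | 91% |
| Direct effect only (.40, 0, .40), no screening | 8% | 99% |
| Same, with screening | 4% | 12% |
| Direct effect only (.25, 0, .30), no screening | 7% | 79% |
| Same, with screening | 3% | 5% |

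Simulation error is about √(0.81 × 0.19/400) = 2 percentage points on the first row. A repeat with 300 trials per scenario gave 80–99% against 6–8% for complete mediation, 80–100% against 79–93% for partial mediation, and about 10% and 5% as written for the two screened direct-effect cases. A further repeat with percentile intervals gave about 13% and 5% for those two cases.

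**Step 4: why screening matters in one case and not the other.** The bivariate slope of y on m is b + c × (a/4)/(1 + a²/4), with a standard error near 1/√500 = 0.045.

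- Complete mediation: the slope is 0.30, more than six standard errors, so the screen is always passed and gives no protection.
- Direct effect only: the slope is 0.40 × (0.10/1.04) = 0.038 in the first case and 0.30 × 0.0615 = 0.018 in the second. Both are below one standard error, so the test is seldom reached.

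**The case against.** The strongest reply is that this is one transposed phrase. The rest of the text fixes the direction: the opening list calls beliefs the mediator, the next paragraph runs from Wave 2 beliefs to Wave 4 outcomes, and Aim 1 gives the same order. Harm requires an analyst to model a randomised assignment as a consequence of later beliefs, and nothing in the documents suggests that anyone intends this. The analysis is also exploratory. All of this stands. It makes a slip the likely explanation and limits the importance of the point, but it does not make the estimation sentence correct.

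A reader might infer something stronger: that the trial would report the opposite of the truth about mediation. The documents do not support that as a general result, for two reasons.

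- The very high false-declaration rates with a direct effect only (79% and 99%) ignore the plan's own screening step. With it they fall to about 5–10%, or up to 13% in repeat runs.
- Under partial mediation both versions usually give the same yes/no answer.

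What survives is a wrong estimand, a near-total loss of power when beliefs carry the whole effect, and an estimate of the wrong size and sometimes the wrong sign otherwise.

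**Conclusion.** The mediation text contradicts itself, and the operative sentence has the path reversed. Followed literally, it would miss complete mediation by beliefs almost entirely (declared in about 6–8% of trials, against 80–99% for the intended product), and under partial mediation it would usually reach the same yes/no answer with a distorted estimate. False claims of mediation are largely held back by the screening step.

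That the sentence estimates a different quantity follows from its wording and the visit schedule. The percentages rest on assumed path sizes, continuous outcomes, unit error SDs, 500 completers and a bivariate reading of the screen. The intended analysis can be recovered from the surrounding text. The randomised comparisons under Hypothesis 1a do not depend on this sentence.

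**What to change.** Replace the estimation clause with: *estimating the indirect effect of intervention condition (randomised at Wave 1) on each Wave 4 outcome through Wave 2 nicotine beliefs, as the product of the condition-to-belief path and the belief-to-outcome path adjusted for condition*. Keep the "bias-corrected bootstrapping method with 1,000 resamples" and the existing interval rule, applied to that product. Writing out the two regressions (beliefs on condition; outcome on beliefs and condition) would remove any remaining doubt. If the lab study uses the same text, make the same change there.

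The cost is one sentence of SAP wording and, optionally, two equations. No new data, visits or participants are needed.

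### Exploratory mediation calls rest on 1,000 bootstrap resamples, so a few per cent would change on rerunning, and estimating indirect effects only after a p<.05 screen inflates them if the belief-outcome link is weak

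*Combined protocol and SAP*

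**What the plan says.** The rule is in the Statistical Analysis Plan, under Analytic Approach, in the paragraph on the second exploratory area (mediation). Wave 2 nicotine beliefs are first related to each Wave 4 outcome by bivariate statistics and regression. The next step is conditional: "Where these preliminary steps indicate potential correlation between nicotine beliefs and study outcomes ($p < .05$), we will test for mediation". The indirect effect is then estimated "using a bias-corrected bootstrapping method with 1,000 resamples", and 95% intervals "that do not include zero will be interpreted to indicate significant mediation". The plan justifies the method as "providing higher power and better control over the Type I error rate versus traditional approaches to test mediation".

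No random seed or stability check is specified. Nothing is said about reporting indirect effects for outcomes that fail the screen. The section is labelled as exploratory ("Exploratory analyses will focus on three areas"). The Sample Size paragraph sets the scale of the data: "Power for Aim 1 was calculated for 715 adults with 70% retention at 12-weeks follow-up", and an expected final sample of 500.

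**The concern.** There are two separate issues.

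**Simulation error.** The verdict turns on which side of zero one interval endpoint falls. With 1,000 resamples, each 2.5% tail holds about 25 values, and the bias-correction term is estimated from the same resamples. Where an endpoint lies near zero, the call of significant mediation can depend on the seed rather than the data.

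**Selection.** If the indirect effect is estimated only where the belief-outcome association reached p<.05, the estimates that exist come from associations that cleared a threshold. When the true association is weak, those that clear it do so partly by chance, and the indirect effect built from them is too large on average.

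At stake is how far the exploratory account of whether belief change carries the intervention's effect can be reproduced and read at face value.

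**Working it through.** **Inputs from the documents.** N = 500 analysed; 1:1 allocation (Study Protocol); detectable effect d = 0.25 to 0.27 (Sample Size); 1,000 bias-corrected resamples, p<.05 screen and zero-exclusion rule (mediation paragraph).

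**Assumptions.** Two-sided alpha of 0.05 for power. Intervention effect on beliefs a = 0.25 SD. Standardised belief-outcome slope b from 0.05 to 0.30, because the documents give none.

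**1. The plan's own figure.** 715 × 0.70 = 500.5. With 250 per arm, power is 79.8% at d = 0.25, which reproduces the stated 80%, and 85.5% at d = 0.27. The plan gives no power or precision figure for mediation.

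**2. Simulation error of an endpoint.** The Monte Carlo SE of the 2.5% point, in units of the estimate's SE, is √(0.025 × 0.975 / B) / φ(1.96), with φ(1.96) = 0.0584.
- B = 1,000: 0.00494 / 0.0584 = 0.084
- B = 5,000: 0.038
- B = 10,000: 0.027

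Error in the bias-correction term comes on top: 2 × √(0.25 / B) / φ(0) = 0.079 at B = 1,000 and 0.025 at B = 10,000. Both terms shrink by √10 = 3.16, a reduction of 1 − 1/3.16 = 68%. The share of verdicts that change should fall by about the same proportion.

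**3. How often two runs disagree.** Trials with N = 500 and a = 0.25 were simulated (1,200 datasets per row), each bootstrapped twice with B = 1,000. The last column is pass rate × disagreement among those passing.

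| b | Two runs disagree | Pass screen | Disagree among those passing | Disagree and pass, % of all tests |
|---|---|---|---|---|
| 0.05 | 4.8% | 20.8% | 4.8% | 1.0% |
| 0.10 | 5.2% | 60.5% | 3.4% | 2.1% |
| 0.15 | 3.4% | 91.9% | 2.7% | 2.5% |
| 0.20 | 3.0% | 99.8% | 3.0% | 3.0% |
| 0.30 | 4.1% | 100% | 4.1% | 4.1% |

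The SE of the 4.1% is √(0.0408 × 0.9592 / 1,200) = 0.6 points. A repeat simulation at a = 0.25 gave 2.8 to 5.1% before the screen and 0.9 to 2.9% of all tests after it, so 3 to 5% and 1 to 3% are fair summaries. At a = 0.40, b = 0.20 disagreement is 0.2%.

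With B = 10,000, disagreement before the screen fell from 3.4% to 1.6% (b = 0.15, 250 datasets) and from 3.0% to 0.0% (b = 0.20, 200 datasets). The repeat simulation gave about 0.9 to 1.6%. These runs are small but consistent with step 2.

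Four belief scales × five constructs (attitudes, norms, behavioural control, intention, behaviour) is 20 tests. At 1 to 3%, that is 0.2 to 0.6 changed verdicts if mediation of this size exists throughout. Separate product-specific intentions or use measures would raise the count.

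**4. What the screen does to the estimates.** With slope SE s = 0.045 (about 1/√500) and k = 1.96 − b/s, the mean slope given passing is b + s × φ(k) / [1 − Φ(k)].
- b = 0.06: k = 0.627; 0.06 + 0.045 × 1.235 = 0.116, ratio 1.93
- b = 0.12: k = −0.707; 0.12 + 0.045 × 0.409 = 0.138, ratio 1.15
- b = 0.15: k = −1.373; 0.15 + 0.045 × 0.170 = 0.158, ratio 1.05
- b = 0.20: k = −2.484; 0.20 + 0.045 × 0.018 = 0.201, ratio 1.004

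For the indirect effect itself, the simulated mean among outcomes passing, divided by the truth, is 2.25, 1.28, 1.03, 0.99 and 1.00 at b = 0.05, 0.10, 0.15, 0.20 and 0.30. At b = 0.15 the unscreened mean in that run happened to be 0.979 of the truth, so the screen's own contribution is 1.0296 / 0.9791 = 1.05, matching the formula.

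**5. What the screen does to false positives.** With a = 0.25 and b = 0, the bias-corrected interval excludes zero in 7.1% of datasets. Requiring the screen as well lowers this to 4.4%.

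**The case against.** **Only an exploratory analysis is affected.** Hypotheses 1a and 1b do not depend on mediation. The assumed 0.25 SD is the smallest effect the trial can detect with 80% power, and the Sample Size paragraph says the pilot effects for nicotine and NRT beliefs were larger. Verdicts change mainly where an interval ends close to zero, which a reader can see. All of this stands, and it keeps the point minor.

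**A reader might infer that the reported effects are inflated in general.** The documents do not support that. They give no belief-outcome slope, and from 0.20 upward the screen has no measurable effect. Most of the inflation among significant results would arise without it: the ratios to truth for b = 0.05 to 0.30 are 2.30, 1.34, 1.12, 1.08 and 1.09 without the screen, and 2.51, 1.40, 1.13, 1.08 and 1.09 with it. Nor does the plan say that belief-outcome associations failing the screen go unreported. It examines those for all listed outcomes, and the screen governs only the mediation step.

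**A reader might also infer that the screen should simply be removed.** Step 5 argues against that: with a zero slope, false mediation calls would rise from 4.4% to 7.1%. The bias-corrected interval alone also gave 7.9% when a = 0 and b = 0.30, which sits poorly with the plan's statement about Type I error, so widening the set of significance tests would not be free.

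**Conclusion.** The point holds in a limited form. With 1,000 resamples, about 3 to 5% of mediation verdicts would differ between two runs on the same data at the design effect size, about 1 to 3% of all tests after the screen, and close to none for clear effects. This rests on a = 0.25 SD, N = 500 and b between 0.05 and 0.30.

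Inflation from the screen is conditional on a weak slope. It matters at about 0.10 to 0.12 or less (15% at 0.12, 28% at 0.10, more than double at 0.05), is 3 to 5% at 0.15, and is negligible from 0.20. Which case applies cannot be settled from the documents. This is a worthwhile improvement to an exploratory analysis, not a flaw that threatens the trial's main conclusions.

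**What to change.** In the mediation paragraph of the SAP:

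1. Replace 1,000 resamples with at least 10,000, and state that the random seed will be fixed and recorded.
2. State that the indirect effect and its 95% CI will be reported for every belief scale and every Wave 4 construct named in that paragraph, whether or not the belief-outcome association reached p<.05.
3. Keep the p<.05 step as a condition for calling mediation significant, and make no significance statement for outcomes that fail it.

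The cost is minutes of computing and a longer exploratory table. No new data or design change is needed.
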